Outpatient cardiology and internal medicine providers in the Yale health system will be selected for potential participation in the study based on the frequency with which they see patients who meet the inclusion criteria (must see at least 10 potentially eligible patients per week). They will be identified based on a retrospective review of clinical encounters that include patients at very high risk for ASCVD events based on clinical guidelines within Epic and approached for consent to participate in the study. Once consented, we will determine baseline prescribing patterns for lipid lowering therapy (over 3months) specifically looking at the proportion of very high risk ASCVD patients on high-intensity statin therapy, ezetimibe, or PCSK9 inhibitor as well as distribution of LDL-C. All physicians will then be randomized within Epic to either the intervention group or the control (usual care) group via a permutated block randomization scheme to ensure an equal number of providers in each study arm. Logic checks within the alerts ensure that once a provider is assigned to an arm, they remain in that arm for the remainder of the study. This will create 100 clusters (providers) to which eligible patient participants will be assigned upon their outpatient visit. In other words, any patient seen by a provider randomized to the intervention (alert) group will have an informational alert generated when their provider opens the order entry screen in the patient's medical record. On the contrary, any patient seen by a provider randomized to the control arm will not generate an alert and will receive usual care. Instead, a "silent alert" that simply registers the patient into the trial by the study team is generated. Because it is likely that providers may internalize the best practice metrics once repeatedly exposed to the alert, cluster randomization of patients at the level of the provider will ensure that providers consistently receive an alert or not, which will reduce contamination between study arms. It will also minimize the chance that providers get so accustomed to seeing an alert for hyperlipidemia that they will become less attentive to the condition in patients not generating an alert. Additional pre- and postintervention analyses in the control group, leveraging the three-month baseline period, can assess the level of contamination and the effect of secular trends towards better care over time.

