We will recruit and consent 100 providers who practice Cardiology and Internal Medicine at or associated with one of the 4 teaching hospitals of the Yale New Haven Health System (to include Yale New Haven Hospital and St. Raphael's Campus, Bridgeport Hospital, and Greenwich Hospital). These practices may be located on site or at satellite offices across the health care system. Providers will be selected based on the number of hyperlipidemia patients seen, on average, to increase efficiency of our study and more quickly reach our target patient enrollment number (see below). These providers will be selected through retrospective review of records from outpatients within the Yale New Haven system and must see a minimum of 10 eligible patients per week. While providers will be recruited to the study and randomized, the aim of the study is to assess the efficacy of alerts on improving the care of patients with hyperlipidemia. Thus, this population of patients will be participants in the study. Our best practice alert will identify patients who meet specific inclusion and exclusion criteria (outlined below), for a target sample size of 2500. These patients will have an alert

generated in their medical record to inform their provider of the presence of very high risk for ASCVD events and elevated LDL-C. Because the study presents minimal risk to patients, we will be requesting a waiver of informed consent at the patient level.

3. **Subject classification:** Check off all classifications of subjects that will be specifically recruited for enrollment in the research project. Will subjects who may require additional safeguards or other considerations be enrolled in the study? If so, identify the population of subjects requiring special safeguards and provide a justification for their involvement.

□Children	□ Healthy	□Fetal material, placenta, or dead fetus
□Non-English Speaking	Prisoners	Economically disadvantaged
persons		
□Decisionally Impaired	Employees	Pregnant women and/or fetuses
□Yale Students	Females of child	dbearing potential

NOTE: Is this research proposal designed to enroll children who are wards of the state as potential subjects?

Yes 🗆 No 🖾

4. **Inclusion/Exclusion Criteria:** What are the criteria used to determine subject inclusion or exclusion?

For patients:

Inclusion Criteria

- Adults 18 years old or greater

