Other aggregate analyses (any report containing Safety data generated during the course of the study)	At the time of Sponsor submission to any body governing research conduct (eg. RA, IRB etc.)	NASCR Manager
 Final (End of Study Report, including): Unblinding data for blinded studies Reports of unauthorized use of a marketed product 	At the time of Sponsor submission to any body governing research conduct (eg. RA, IRB etc.) but no later than 1 calendar year of study completion	NASCR Manager

9. Statistical Considerations:

Initial review of retrospective data for calendar year 2017 revealed 35,472 unique individuals who underwent LDL testing at a Yale-affiliated practice. Of those, 4,451 had ASCVD (one ICD-10 code) and LDL-C > 70mg/dL. The following graphic displays the cumulative number of unique eligible patients attained (y-axis) by interfacing with a given number of providers (x-axis), starting with the provider who sees the most patients meeting inclusion criteria.

As displayed above, clusterrandomization of the top 100 providers (in terms of number of patients with high-LDL seen; at least 10 per week) would include approximately 3700 unique patients and we are proposing to enroll 2500 patients over 9 months. Randomizing 100 providers (50 in the alert group and 50 in the control group with an equal number of cardiology and internal medicine providers in each arm - 25 patients per provider) would give 80% power to detect a difference in intensification of lipid lowering therapy from 5% (current ezetimibe rate) to 9.3% and 90% power to detect a difference from 5% to 10.7%, assuming

a conservative intra-class correlation coefficient of 0.05. Similarly, we would have 80% power to detect an increase in PCSK9 inhibitor use from <0.2% to 1.9% and 90% power to detect an increase from <0.2% to 2.4%. The primary analysis will be conducted using logistic regression where the independent variable (primary endpoint) is the proportion of the patients who have intensification of their lipid lowering therapy and the primary dependent variable is randomization status. The regression will be clustered at the provider level.

SECTION II: RESEARCH INVOLVING DRUGS, BIOLOGICS, RADIOTRACERS, PLACEBOS AND DEVICES

If this section (or one of its parts, A or B) is not applicable, check off N/A and delete the rest of the section.

A. RADIOTRACERS MN/A

B. DRUGS/BIOLOGICS MN/A

B. DEVICES **N/A**

SECTION III: RECRUITMENT/CONSENT AND ASSENT PROCEDURES

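### Equal cardiology and internal medicine numbers in each arm are stated as part of the design, but the described randomisation does not secure them

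*Combined protocol and SAP*

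**What the plan says.** Section I, item 9 (Statistical Considerations) gives the design behind the power figures. It divides the 100 providers evenly between the two arms and describes the arms as formed "with an equal number of cardiology and internal medicine providers in each arm". The assumed cluster size is "25 patients per provider".

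The Research Plan says that consenting providers are randomised within Epic "via a permutated block randomization scheme to ensure an equal number of providers in each study arm". No stratification factor, block size or list order is given.

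On selection, Section I, item 2 (Subject Population) says: "Providers will be selected based on the number of hyperlipidemia patients seen". The Research Plan and items 2, 4 and 5 all set a minimum of ten eligible patients per week. Item 9 refers to the top 100 providers by patient volume. None of these sections sets a number to be recruited from each specialty.

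The primary analysis in item 9 is a logistic regression of intensification on randomisation status, clustered by provider. No other covariate is named.

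**The concern.** The statement in item 9 can mean 25 cardiology and 25 internal medicine providers in each arm, or the same specialty mix in both arms. Permuted blocks that equalise total numbers guarantee neither. The first meaning also needs an overall pool of exactly 50 and 50, which selection by volume does not ensure.

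The two specialties may intensify lipid therapy at different rates; the documents give no rates by specialty. If they do differ, an uneven split moves the observed arm contrast in the trial as run, and the primary model has no term to take this out. A reader of item 9 would also credit the trial with a balance that its described procedures do not create.

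**Working it through.** **1. The plan's own power figure.** Inputs from item 9: 50 providers per arm, 25 patients each (1250 per arm), ICC 0.05, rates 5% and 9.3%. Alpha is not stated; I assume 0.05 two-sided.

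- Design effect: 1 + (25 − 1) × 0.05 = 2.2.
- Effective size per arm: 1250 / 2.2 = 568.2.
- Power of the two-proportion test with pooled variance under the null: 80.4%.

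The stated 80% reproduces, and specialty is not an input. (By the same method, 5% versus 10.7% gives 94.7% rather than the stated 90%. That is a separate matter and has nothing to do with specialty.)

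**2. Chance of balance without stratification.** Assume a pool of 50 cardiology and 50 internal medicine providers, with list order unrelated to specialty. The number of cardiology providers in the alert arm is then approximately hypergeometric (100 providers, 50 cardiology, 50 drawn), with SD 2.5.

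| Split of cardiology providers between arms | Probability |
|---|---|
| Exactly 25:25 | 15.8% |
| 28:22 or worse, either direction | 31.7% |
| 29:21 or worse | 16.1% |
| 30:20 or worse | 7.1% |

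Simulated unstratified blocks of 2, 4 and 10 agree: 15.5% to 16.1% for the exact split and about 7% for 30:20 or worse. If the pool were 30:70 or 70:30, an equal split of each specialty between arms would have probability 17.2%, and 25 + 25 within each arm would be impossible.

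**3. Effect of a 30:20 split.** With no alert effect, the arm difference is (30/50 − 20/50) × (cardiology rate − internal medicine rate). The specialty rates are assumptions chosen to average the stated 5%.

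| Assumed cardiology / internal medicine rates | Shift in arm contrast | Share of the 4.3-point target (9.3 − 5) |
|---|---|---|
| 6% / 4% | 0.2 × 2 = 0.4 points | 9% |
| 7% / 3% | 0.2 × 4 = 0.8 points | 19% |
| 8% / 2% | 0.2 × 6 = 1.2 points | 28% |

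Standard error of the arm difference at 5%: √(2 × 0.05 × 0.95 / 568.2) = 1.29 points. All three shifts are smaller.

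**4. Is this variation already in the plan?** The between-specialty variance is the square of half the rate gap. Divided by 0.05 × 0.95 = 0.0475, it contributes to the ICC:

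- 6%/4%: 0.01² / 0.0475 = 0.002
- 7%/3%: 0.02² / 0.0475 = 0.008
- 8%/2%: 0.03² / 0.0475 = 0.019

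All lie within the planned 0.05.

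**5. What stratifying and adjusting could recover.** Suppose the planned 0.05 includes the specialty share and that share is removed. The design effect 1 + 24 × (0.05 − share) becomes 2.15, 2.00 or 1.75, and power for 5% versus 9.3% becomes about 81%, 84% or 89%. This is a normal approximation.

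**The case against.** The strongest reply is that item 9 is itself part of the plan. Its sentence can be read as the requirement, with the Research Plan giving the method only in brief. The Research Plan does not say that the blocks are unstratified, and a list sorted by specialty would come out nearly balanced anyway. This is possible, and it is why the probabilities above are conditional. But the only stated aim of the blocks is equal totals, so the property still has no stated mechanism.

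The reply is right on several stronger readings that a reader might infer:

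- **That the power calculation rests on specialty balance.** It does not. The 80% reproduces without any specialty input.
- **That imbalance would bias the trial.** Under valid randomisation it is sampling variation between providers, which the ICC and the provider-level clustering are there to cover.
- **That the selection sections rank both specialties in one pool.** The Research Plan and items 2, 4 and 5 set a volume threshold, which would allow a fixed number from each specialty. Only item 9 refers to a top 100.
- **That a cardiology versus internal medicine comparison is put at risk.** The documents plan none.

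It is also fair to say that missing an exact 25:25 split counts even 26:24 as a failure, and that 30:20 or worse has a probability of only about 3.5% in each direction.

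**Conclusion.** The point holds in a limited form. The documents state a specialty balance within each arm that their only described allocation method does not secure, and the primary model has no specialty term to make up for it.

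If the blocks are unstratified and the pool is 50:50, the exact balance occurs about 16% of the time, and a split of 30:20 or worse about 7%. At 30:20 the arm contrast moves by 0.4 to 1.2 points over the assumed rates, under one standard error. Those rates are illustrations; the documents give none by specialty.

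The sample size and the 80% power stand. What is lost is some precision, protection against an unlucky draw and the accuracy of a design statement. This goes a little beyond missing detail, because a better method is available at almost no cost.

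**What to change.** If randomisation has not been done:

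- Stratify the permuted blocks by specialty, with one list for cardiology and one for internal medicine, and say so in the Research Plan.
- Add specialty as a covariate in the primary provider-clustered logistic model.
- Reword item 9 to say that providers are balanced between arms within specialty.

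If it has been done, correct item 9, report the actual specialty split by arm, and adjust for specialty in the primary model.

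The cost is a second randomisation list and one model term. Specialty is known before providers are randomised, and no extra patients or data are needed.

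A quota of 50 providers from each specialty is needed only if 25 + 25 per arm is truly intended. It would depart from the top-100 selection behind the estimate of about 3700 eligible patients, so its effect on that yield should be checked first.

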Once a patient is seen by an enrolled-provider, they will not generate further alerts. This ensures that the rare patient who is seen by two providers from different arms of the study cannot be enrolled twice.

Identification of patients to be involved in the study and generation of an alert (or not) will be performed entirely within the Epic medical records system based on inclusion and exclusion criteria outlined below. This will be done using a best-practice alert build developed by the data analytics team at Yale that will, upon opening the order entry screen in the patient's chart by a enrolled provider, examine the medical record to identify the patient as having very high risk for ASCVD (see ICD-10 codes below) as well as an LDL-C > 70mg/dL without a recent change in lipid lowering therapy (dose escalation or addition of new therapy). If these conditions are met, the patient will be included in the study and then depending on whether the provider is randomized to the alert or usual care arm, will determine whether an alert is shown upon entering the order screen within the medical record.

Providers in the intervention (alert) group will have an alert generated within the electronic medical record system for all patients who meet criteria. The alert will fire once per patient, during the patient's first eligible outpatient visit, when the provider opens the order entry screen in the patient's electronic medical record. This will maximize the chance that the alert appears at the most relevant place in the provider's workflow. There will be a 1-hour lockout feature such that a provider randomized to receiving alerts will not receive another alert within 1 hour but outside that window would receive another alert for the patient if they enter the order page of the record.

The alert will consist of a "pop-up" that notifies the physician that the patient is at very high risk for ASCVD events, displays the most recent cholesterol values and current lipid lowering therapy. In addition to noting that the provider should ensure adherence to both current lipid-lowering therapy and lifestyle modifications, a link to full treatment guidelines for hyperlipidemia is also provided and includes a continuing medical education (CME) option to obtain CME credits. An example of what this alert will look like is as follows:

) Patient May Need Lipid Me	dication Optimization		
Your patient has clinical ath	erosclerotic cardiovascular disease (/	SCVD)	

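### The stated 80% power holds only if each of the 100 providers contributes exactly 25 patients; the calculation has almost no slack and makes no allowance for unequal clusters

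*Combined protocol and SAP*

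**What the plan says.** Section I, item 9 (Statistical Considerations) randomises 100 providers, "50 in the alert group and 50 in the control group". The power statement is "25 patients per provider) would give 80% power to detect a difference in intensification of lipid lowering therapy", specifically "from 5% (current ezetimibe rate) to 9.3"%. A second figure follows: "90% power to detect a difference from 5% to 10.7"%. Both rest on "a conservative intra-class correlation coefficient of 0.05". The analysis is a logistic regression clustered by provider. Alpha, sidedness and variation in cluster size are not mentioned.

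On accrual, the same item says the top 100 providers "would include approximately 3700 unique patients and we are proposing to enroll 2500 patients over 9 months". The graphic of 2017 data behind this adds providers in order, "starting with the provider who sees the most patients meeting inclusion criteria".

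The Research Plan says that providers in the alert arm "will have an alert generated within the electronic medical record system for all patients who meet criteria". Control providers' patients are registered by a silent alert. Section I, item 5 makes enrolment automatic, under the treating provider. Permuted blocks equalise the number of providers per arm, and item 9 adds equal numbers from each specialty. Neither balances patient volume. No limit on patients per provider is stated.

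**The concern.** In a cluster trial with a fixed total and a fixed ICC, precision is best when clusters are equal. Under a provider-clustered regression, large clusters add correlated patients and small ones do not make up for them. Here 25 is simply 2,500 / 100. It is an average that the calculation treats as a common size.

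The mechanism described will not produce a common size. Each provider contributes however many eligible patients arrive before the total is met, and volumes will differ between providers and between two specialties. Even if all 100 providers had the same expected volume, chance variation in counts averaging 25 would give a CV of about 1/√25 = 0.2.

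What is at stake is how the primary result is read. A null finding would be described as coming from a trial with 80% power for 5% versus 9.3%, when that figure omits a foreseeable loss.

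**Working it through.** **Inputs from Section I, item 9:** 50 providers per arm; mean cluster size m = 25, so 1,250 patients per arm; ICC = 0.05; rates 5% and 9.3%. **Assumed:** two-sided alpha 0.05; no dropout (none is stated); a range for CV.

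**Step 1: reproduce the stated figure.**
- Design effect = 1 + (25 − 1) × 0.05 = 2.20.
- Effective n per arm = 1,250 / 2.20 = 568.2.
- Mean rate = (0.05 + 0.093) / 2 = 0.0715.
- z = [0.043 × √568.2 − 1.96 × √(2 × 0.0715 × 0.9285)] / √(0.05 × 0.95 + 0.093 × 0.907) = (1.025 − 0.714) / 0.363 = 0.856.
- Power = 80.4%. Variants give 80.6% (unpooled variance) and 79.8% (t with 98 df).
- The rate detectable at 80% power is 9.27%.

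The figure therefore reproduces with equal clusters. The margin is thin: at ICC 0.05, power falls below 80% once CV passes about 0.13.

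**Step 2: allow unequal clusters, holding 2,500 patients and ICC 0.05.**
Design effect = 1 + ((1 + CV²) × 25 − 1) × 0.05. At CV 0.5, for example, this is 1 + (31.25 − 1) × 0.05 = 2.513, so effective n = 1,250 / 2.513 = 497.5.

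| CV | Design effect | Effective n per arm | Power, 5% vs 9.3% | Rate detectable at 80% power |
|---|---|---|---|---|
| 0 | 2.20 | 568.2 | 80.4% | 9.3% |
| 0.2 | 2.25 | 555.6 | 79.5% | 9.3% |
| 0.3 | 2.31 | 540.5 | 78.4% | 9.4% |
| 0.4 | 2.40 | 520.8 | 76.9% | 9.5% |
| 0.5 | 2.51 | 497.5 | 75.0% | 9.6% |
| 0.6 | 2.65 | 471.7 | 72.7% | 9.8% |
| 0.8 | 3.00 | 416.7 | 67.4% | 10.1% |

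Power drops below 78% once CV passes about 0.33.

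**Step 3: check by simulation.** Beta-binomial outcomes, 100 clusters, 2,500 patients, ICC 0.05 and cluster-robust logistic regression with a t reference (6,000 runs per CV) gave 78.9% at CV 0, 76.4% at 0.3, 74.2% at 0.5 and 69.0% at 0.8. The pattern is the same.

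**Step 4: an efficiently weighted mixed model.** Relative efficiency = 1 − CV² × λ(1 − λ), with λ = 25 / (25 + 0.95/0.05) = 25/44 = 0.568. At CV 0.5 this is 1 − 0.25 × 0.245 = 0.939, so effective n is about 533 and power 77.9%. Power is 79.5% at CV 0.3, and it drops below 78% only above CV of about 0.49.

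**Step 5: other ICC values, by the Step 2 formula.** ICC 0.04 with CV 0.5 gives a design effect of 1 + 30.25 × 0.04 = 2.21 and power of 80.2%. ICC 0.03 with CV 0.8 gives 1 + 40 × 0.03 = 2.20 and power of 80.4%.

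**The case against.** The strongest reply is that the documents do not give the CV, so no particular shortfall can be asserted. That stands. A reader might infer that the trial lacks 80% power by a material amount. The documents do not support this: up to CV of about 0.33 the loss stays within about two points of 80%, and the graphic that would settle the matter is not available here.

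A reader might also infer a large CV from the volume ranking. That does not follow either. The ranking wording describes how the graphic is ordered, and choosing the busiest providers may narrow the low end of the distribution. The floor of 10 eligible patients per week is weak evidence of narrowness, though. It sits beside about 3,700 / 100 = 37 unique patients per provider in the 2017 data, so it cannot be counting unique enrollable patients.

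A third tempting reading is that enrolment is open-ended. It is open-ended per provider only, because the total is targeted at 2,500. Enrolling all 3,700 would give 85.9% with equal clusters and at least 80% up to CV of about 0.51, but that is not the plan.

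The plan calls its ICC conservative, and Step 5 shows that a lower value would absorb a moderate CV. No justification for the word is given, however, and the stated claim is 80% at 0.05. The analysis description does not settle robust errors versus a mixed model, so the smaller loss in Step 4 remains possible.

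Finally, the 90% figure for 10.7% has room: 94.8% with equal clusters and 90.4% at CV 0.6. It does not show that a CV was built in, because CV 0.6 gives only 72.7% for 9.3%.

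**Conclusion.** The concern holds as an omitted allowance. The 80% is correctly computed for 100 equal clusters of 25, has almost no slack, and rests on a condition the enrolment mechanism will not meet. At the plan's own total and ICC, power for 5% versus 9.3% falls from 80.4% to between 79.5% (CV 0.2) and 67.4% (CV 0.8), and the detectable rate rises from 9.3% to as much as 10.1%. The loss is smaller with an efficiently weighted mixed model or an ICC below 0.05.

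These figures assume two-sided alpha 0.05, no dropout and the CV range shown. How far actual power falls below 80% cannot be established from the documents. The primary analysis remains valid; what needs correcting is the stated power.

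**What to change.** In Section I, item 9:
- Compute the CV of cluster size from the per-provider 2017 counts behind the graphic, and report it.
- Restate power and the detectable difference using 1 + ((1 + CV²) × 25 − 1) × ICC. If a mixed model is the planned analysis, say so and use its equivalent.
- State the alpha and sidedness used.

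This is a recalculation from counts the investigators already hold, with no change to conduct. The downside is a slightly less favourable stated power. A per-provider cap is not recommended here, because it would slow accrual and is a trade-off that restating the figure avoids.

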Our primary outcome will be proportion of patients with intensification of lipid lowering therapy, defined by an increase in statin dose, addition of ezetimibe, or addition of PCSK9 at 90-days. The key secondary endpoint will be the achieved LDL-C (fasting or non-fasting¹¹) at 6-months. Other outcomes

of interest will be the proportion of patients with an LDL-C <70 mg/dL and the proportion with an LDL-C <55 mg/dL. An exploratory endpoint, in an optional extension phase, we will assess the rates of long-term outcomes, specifically the rate of major adverse cardiac events (MACE) defined as hospitalization for myocardial infarction, cerebrovascular accident/transient ischemic attack, or coronary or peripheral arterial revascularization. All outcomes will be abstracted from the patient chart via medical record review.

Additional outcomes will collect provider education and experience metrics. We will assess the percentage of providers who visit the guideline site via the link provided within the alert. Further, all providers will be asked to complete both a pre- and post- study survey that will assess their knowledge of and the level of comfort with the ACC/AHA guidelines for hyperlipidemia. The post survey will also include questions that will allow us to assess provider approval and overall acceptance of the alert, assessing their opinions on user friendliness, usefulness versus disruptiveness, and overall user experience. Analysis of responses will allow us to assess which aspects of the alert were most helpful and which could be improved in possible future iterations of this alert and others.

Alerts will no longer be seen by providers and removed from Epic once enrollment is complete but may be reinstated should our data and further study prove that such alerts are useful and beneficial to the patient population.

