Objectives and Endpoints: The objective of this study is to evaluate the efficacy of targeted electronic alerts to improve rates of best practices in the treatment of patients with hyperlipidemia who are seen by outpatient cardiology and internal medicine physicians. The primary outcome will be the proportion of patients who have intensification of their lipid lowering therapy (increase in statin dose or addition of ezetimibe or addition of a PCSK9 inhibitor) at 90-days. The secondary outcomes will be achieved LDL-C (fasting or non-fasting) at 6-months and rates of hospitalization for myocardial infarction, stroke, unstable angina, coronary or peripheral artery revascularization.

Consent and Survey distribution: Provider consent will be collected in one of several ways, and we are requesting a waiver of documentation of consent for providers in this study, as the study poses minimal risk. The first method for provider outreach and consent will be done through university email in which a link to the consent and provider survey will be provided. In this method, the consent and survey will be administered electronically via REDCap (Research Electronic Data Capture) and an electronic signature will be captured. This link to the consent form will be sent to all eligible providers that will direct them to our online consent form in REDCap for review and signature. If the provider consents, we will follow up and send a survey link that will direct them to the survey form in REDCap.

Should provider outreach via email prove difficult, we will use other means to contact eligible providers. The first will be via an Epic inbasket message, where the informed consent will be copied directly into the body of an Epic message that is then sent to the eligible provider. The provider can then read through the consent and reply back to the inbasket message with "Yes I do consent" or "No I do not consent", without requiring a signature on the consent document. This response will be document, and consented providers will then be sent further instructions and a link for the REDCap survey.

We will also contact providers via telephone, where study personnel will describe the study via phone, answer questions, and receive and document provider verbal consent. Consented providers will then be sent further instruction and a link for the REDCap survey.

If/when feasible, study coordinators will also conduct in-person recruitment to obtained signed consent.

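### The 90% power claim (5% to 10.7%) conflicts with the plan's own inputs, which give about 95%, and the 5% control rate is labelled for one component of the composite primary endpoint

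*Combined protocol and SAP*

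**What the plan says.** Section I, item 9 gives the design as "Randomizing 100 providers (50 in the alert group and 50 in the control group"), with 25 patients per provider, 2,500 patients in all and "a conservative intra-class correlation coefficient of 0.05". From this it claims 80% power to detect a change in "intensification of lipid lowering therapy from 5% (current ezetimibe rate) to 9.3% and 90% power to detect a difference from 5% to 10.7" percent. It makes a parallel claim for one drug class, 80% power for "an increase in PCSK9 inhibitor use from <0.2% to 1.9" percent, and 90% power for a rise to 2.4%. Alpha and sidedness are not stated.

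Objectives and Endpoints defines the primary outcome as the proportion of patients with "intensification of their lipid lowering therapy (increase in statin dose or addition of ezetimibe or addition of a PCSK9 inhibitor) at 90-days". The outcomes paragraph of the Research Plan agrees: "defined by an increase in statin dose, addition of ezetimibe, or addition of PCSK9 at 90-days".

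The study-flow part of the Research Plan describes a three-month baseline, "specifically looking at the proportion of very high risk ASCVD patients on high-intensity statin therapy, ezetimibe, or PCSK9 inhibitor". It also mentions pre- and post-intervention "analyses in the control group, leveraging the three-month baseline period", to assess contamination and secular trend. Neither is linked to the power calculation.

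**The concern.** There are two separate difficulties.

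**The two power claims.** They share one design, one control rate and, presumably, one alpha. Under a normal approximation, moving from 80% to 90% power should raise the detectable rate by less than a percentage point here. The plan raises it by 1.4 points, from 9.3% to 10.7%.

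**The control rate.** The 5% carries the label of a single component. It is not clear whether it means the share of patients already taking ezetimibe or the share newly given it in some period. The endpoint counts new events over 90 days and includes statin dose increases, for which the plan gives no rate. If 5% is not the control rate of the composite, the 80% figure answers a different question from the one the trial asks.

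**Working it through.** **Inputs** (Section I, item 9): 50 providers per arm; 25 patients per provider, so 1,250 per arm; ICC 0.05; control rate 5%; alternatives 9.3% and 10.7%. Assumed because not stated: two-sided alpha 0.05, equal cluster sizes, no dropout.

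**Effective sample size.** Design effect = 1 + (25 − 1) × 0.05 = 2.2. Effective n = 1,250 / 2.2 = 568.2 per arm.

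**Formula.** Power = Φ[(d − 1.96 × SE0) / SE1], where d = p2 − p1, SE0 = √[2p̄(1 − p̄)/n], SE1 = √{[p1(1 − p1) + p2(1 − p2)]/n} and p̄ is the mean of p1 and p2.

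**The 80% pair, 5% vs 9.3%.** p̄ = 0.0715, SE0 = 0.01529, SE1 = 0.01523. (0.043 − 0.02996) / 0.01523 = 0.856, so power is 80.4%. The plan's figure is reproduced.

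**The 90% pair, 5% vs 10.7%.** p̄ = 0.0785, SE0 = 0.01596, SE1 = 0.01587. (0.057 − 0.03128) / 0.01587 = 1.621, so power is 94.8%. The plan's figure is not reproduced.

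**Other formulas.** Rates giving 80%, 90% and 95% power from 5%:

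| Method | 80% | 90% | 95% |
|---|---|---|---|
| Pooled z | 9.27% | 10.07% | 10.74% |
| Unpooled z | 9.26% | 10.05% | 10.72% |
| t, 98 df | 9.31% | 10.11% | 10.79% |
| Continuity-corrected | 9.48% | 10.27% | 10.95% |
| Arcsine | 9.23% | 10.00% | 10.65% |
| Log odds ratio | 9.36% | 10.20% | 10.93% |

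Across the six, power at 10.7% is 93.5% to 95.3%. A beta-binomial simulation of 20,000 trials gave 94.7% to 95.1%.

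**Could another alpha or ICC rescue both claims?** No.
- Setting alpha so that 10.7% has 90% power needs two-sided 0.0216, and 9.3% then has 69.7%.
- Setting the ICC to do so needs 0.070, and 9.3% then has 72.2%.
- Fixing n so that 9.3% has exactly 80% power, 10.7% has 93.5%, 94.6%, 95.3% or 96.2% at two-sided alpha 0.10, 0.05, 0.025 or 0.01.

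**The PCSK9 inhibitor pairs.** Taking <0.2% as 0.2%, the pooled formula gives 80.3% at 1.9% and 90.7% at 2.4%, matching the plan.

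**Sensitivity to the control rate.** Rates other than 5% are assumptions, and the ICC is held at 0.05 throughout:

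| Control rate | Rate detectable at 80% power (odds ratio) | Power for +4.3 points | Power for odds ratio 1.95 |
|---|---|---|---|
| 5% | 9.3% (1.94) | 80.4% | 80% |
| 10% | 15.5% (1.66) | 60.2% | 97% |
| 15% | 21.4% (1.54) | 48.5% | 99% |
| 20% | 27.0% (1.48) | 41.5% | 99.8% |

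If 5% is the 90-day rate of adding ezetimibe, the composite rate cannot be lower. If 5% is prevalence of use, it does not bound the composite in either direction, and lower rows also apply: 2% to 5.1% (2.61) and 3% to 6.5% (2.26).

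**The case against.** **The arithmetic slip is harmless to the design.** It understates power at 10.7%, and it changes neither the 80% figure nor the sample size. This is right: alone it would be minor, and the control rate carries the weight.

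**The 5% is a disclosed proxy.** The sentence applies 5% to intensification and says in parentheses where it came from, so the plan is open about its assumption. That is fair, but naming a proxy is not evidence that it matches a three-route 90-day composite. The direction of the effect is also undetermined: above 5%, power falls for a fixed absolute gain and rises for a fixed odds ratio. The finding is a missing justification, not a demonstrated shortage of patients.

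**The PCSK9 match depends on the formula.** It holds for the pooled, unpooled and t formulas. The continuity-corrected, arcsine and log-odds formulas give 71.3% and 85.5%, 88.4% and 96.2%, and 63.2% and 72.7%. With about 568 × 0.002 = 1.1 effective control events, none is dependable. This stands, so the match is weak support. The conflict between 9.3% and 10.7% does not need it.

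**Correcting the rate could imply a larger trial.** Keeping a 4.3-point target at 80% power would take about 3,980, 5,300 or 6,440 patients at control rates of 10%, 15% or 20%, with 25 per provider. This also stands: the correction needs no extra patients only if a larger detectable difference is accepted.

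**Conclusion.** The concern holds in both parts and should be fixed.

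First, the stated 90% pair does not follow from the stated inputs. Power at 10.7% is about 95%, given the assumed two-sided 0.05. That the two pairs contradict each other does not depend on this assumption, since no alpha at the stated ICC yields both. Either the rate is wrong (about 10.1% would fit 90%) or the power label is wrong (10.7% fits about 95%), and the documents do not show which.

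Second, the 80% claim is arithmetically sound only if the composite control rate is 5%, and the documents offer no composite rate. Power for the primary endpoint is unverified rather than shown to be inadequate.

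**What to change.** 1. State alpha and sidedness in Section I, item 9. Then either change 10.7% to about 10.1% (if alpha is two-sided 0.05) or relabel 10.7% as the rate detectable with about 95% power. The replacement depends on alpha: at two-sided 0.025 the 90% rate would be 10.6%, and at 0.01 it would be 11.2%.

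2. Say what the 5% measures. Replace it with the 90-day composite intensification rate among the selected providers' eligible patients, and restate the detectable difference. The query should apply the trial's own rules, including the first eligible visit and no recent change in lipid-lowering therapy. The endpoint text should first say whether starting a statin counts as an increase in dose.

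3. Use records earlier than the planned three-month baseline. Each index visit needs a full 90 days of follow-up, and a three-month window gives that only to visits at its start. The planned baseline proportions describe who is on each therapy, not who is intensified.

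4. Until the rate is known, tabulate detectable rates over a range of control rates as above. Include rows below 5% only if 5% is prevalence of use.

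The cost is one further record query and one reworded paragraph. The restated difference may be larger than 4.3 points. It can be smaller only if 5% is prevalence of use and the composite rate is below 5%.
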